older agents. On the other hand, topiramate, levetiracetam, oxcarbazepine are newer agents that are taken frequently for the second-line AEDs. 12, 13 The American Academy of Neurology (AAN) subcommittee reports in 2004 observed that newer AEDs were not different in controlling seizures but have better tolerability, particularly fewer neurotoxic adverse effect.¹⁴-¹⁶ There have been many studies comparing the efficacy and safety between first and secondline AEDs in newly diagnosed epilepsy children, showed that first-line agents are as efficacious as second ones. Guerreiro reported that seizure freedom rate in childhood absence epilepsy treated with phenytoin did not differ from those with oxcarbazepine.¹⁷ A study in Turki explained valproic acid, carbamazepine and phenobarbital have the same efficacy as levetiracetam for newly diagnosed epilepsy children. 18 The results was in line with that was reported by James, that valproic acid, carbamazepine as first-line agents and topiramate as the second one are equally effective to treat newly diagnosed epilepsy children. 19 While for drugresistant epilepsy, previous research investigated that children did not get seizure-free although they have been treated with levetiracetam, known as second-line AED, as add-on therapy.²⁰ However, there is no robust evidence for therapeutic efficacy of first-line AEDs as substitution of second-line ones. When it comes guideline therapy, there has not been any international guideline of combination therapy for the management of drug resistant epilepsy, even though many recommendations that have been made regionally in certain countries.

In the local situation in Indonesia where the study will be conducted, there are some challenges in the management of drug-resistant epilepsy in children. Similar to those in other countries, a study at Cipto Mangunkusumo General Hospital, Jakarta, showed that around 43% and 31% did not get seizure remission children although they have been given topiramate or levetiracetam respectively. Besides, from the factual situation at outpatient pediatric neurology clinic in Jakarta, the capitol of Indonesia, the number of the drugs that were covered by social insurance are limited so that sometimes patients should buy themselves the uncovered drugs that are needed. Moreover, the newer agents are sometimes not available even in the referral hospitals in other cities spreading all over the country.

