Randomized studies in drug-resistant epilepsy typically involve addition of new anti-epileptic drugs. However, in clinical practice, if the patient is already taking multiple drugs, then substitution of one of the current medications commonly occurs, despite little evidence supporting this approach.²² The choice of the substitution drug depends on the mechanism of action, the pharmacokinetic profile, drug-drug interaction, and the risk of seizure exacerbation as well as patients-related factors. The new combination is intended to maximize efficacy and minimize toxicity. However, the availability and cost-effectiveness should also be

taken into consideration since the patient would not reach the goal of ideal combination of drugs if they could not afford it nor even get the medication. ²³⁻²⁶ Another considerable case is one of drug resistance patterns in which at the first-time patients may not responsive to treatment yet they change into a state that is responsive to the medication. ²⁷ The choice of substitution therapy may originate from firs-line AEDs since evidences have shown they have equal efficacy to those of second-line ones. However, there is still lack of evidence whether the drug resistance pattern occur if the substitution drug is originated from first-line AED even more if it has ever been given prior to the current drug combination. ²⁷ The study aims to analyzed the efficacy and safety of first-line AEDs as substitution therapy in drug-resistant epilepsy children.

Primary Objective

The primary outcome of the research is to analyze the proportion of responders, who are defined as subjects who get 50% of seizure reduction.

Secondary Objectives

There are some secondary objectives of the study. The first one is to analyze the differences of improvement of quality of life, EEG feature and time to achieve seizure reduction, between the intervention and the control group. Besides, the research will describe the clinical characteristics, adverse effects of the drugs and laboratory features related to the adverse effects, among children with drug-resistant epilepsy. Furthermore, it will explain factors influencing the reduction of seizure frequency

Study Design

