EEG recording results are categorized into:

- Normal: does not show of hypofunction/asymmetry/epileptiform waves
- Abnormal: shows a picture of hypofunction/asymmetry/epileptiform waves or a combination of 1 or more of these features

The subjects who show changes in their EEG are later grouped into groups of abnormal to normal or abnormalities that showed improvement. Abnormalities that show improvement, for example are hypofunction (slowing down) waves experience improvement or decreasing number of epileptiform waves.

Next, a proportion calculation is carried out in the form of the percentage to subjects who experience a change in the EEG and will be categorized into:

- Different : when a significant difference is shown in difference of proportion test of the group that reuses first line OAE line as substitution therapy and those that use standard therapy/
- Not different: when there is no significant difference is shown in difference of proportion test of the 2 groups.
- d. Difference in actual failure between the groups reusing first line OAE as substitution therapy and those taking standard therapy. Description of drug side effects in the form of frequency distribution and percentage of side effects in each group. Description of laboratory results in the form of frequency distribution and percentage of side effects in each group
- e. Factors contributing to decrease in seizure frequency (age, seizure onset, seizure type, family history of seizures, developmental delay, history of OAE, initial seizure frequency, initial EEG, structural brain abnormalities)

Sample size

The estimated sample size in this study was calculated using the different proportion formula for the 2 unpaired groups as follows ²⁹:

$$n1 = n2 = (\frac{Z_{\alpha}\sqrt{2PQ} + Z_{\beta}\sqrt{P1Q1 + P2Q2}}{P1 - P2})^{2}$$

Description:

n1 number of subjects who received the new drug (First Line OAE)

n2 number of subjects receiving standard drug (Second line OAE)

Alpha type one error (5%)

Zα alpha standard value 5% one-way hypothesis (1,96)

Beta type two error (20%)

Zβ beta default value 20% (0,84)

P2 proportion of decreased seizures on standard drugs (reference) for example 0.7

Q2
$$1-P2 = 1-0.7 = 0.3$$

P1-P2 difference in the proportion of reduced seizure that is considered significant between the new drug and the standard (defined by the researcher) for example 25% (0.25)

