P1 proportion of reduced seizure on the new drug (the proportion of reduced seizure on the standard drug in addition to the minimal difference that is considered significant)= 0.7 + 0.25 = 0.95

Q1
$$1 - P1 = 1 - 0.95 = 0.5$$

P
$$(P1 + P2) / 2 = (0.95 + 0.7) / 2 = 0.825$$

Q
$$1-P = 1-0.825 = 0.175$$

In this study, it was found that the proportion of seizure reduction on standard drugs was 70%.³⁰ Therefore the equation:

$$n1 = n2 = \left(\frac{1,96\sqrt{2(0,825)(0,175)} + 0,84\sqrt{(0,95)(0,5) + (0,7)(0,3)}}{0,25}\right)^2 = 49,56 = 50$$

$$n\ 2\ groups=100$$

Based on the formula above, 100 research subjects are required. An additional of 10% from the total number of subjects are needed as there is a possibility of those dropping out, therefore a total of 110 subjects are needed in this study.

Statistical Analysis

- 1. Analysis of differences in the proportion of responders (primary outcome), differences in EEG appearance (secondary outcome) in pediatric epilepsy patients who are resistant to the combination of second line OAE between those who reused first line OAE as substitution therapy and those who used standard therapy. Data type is categorical. Data is analyzed the Chi-square statistical test, if it does not meet the requirements then an alternative test is performed, known as Fisher's multiple test. The significance level (α) is 5% and the research confidence level is 80%. If p value ≤ α is obtained, this means H0 is rejected, which means that there is a difference seen in seizure frequency between reusing first line OAE as substitution therapy and standard therapy.
- 2. Analysis of differences in the mean quality of life with an unpaired T test if the data distribution is normal or Mann-Whitney if data distribution is not normal
- 3. To assess drug effectiveness, the analysis used was the difference in actual failure between those using first line OAE as substitution therapy and those using standard therapy (primary outcome). Formula:

$$ARR = CER - EER$$

CER: the incidence of increased seizure frequency in the standard therapy group ERR: the incidence of increased seizure frequency in the group in substitution therapy with 1st line OAE The increase in seizure frequency in this study shows therapy

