This test will use 2 analyses known as intention to treat analysis and per-protocol analysis. Intention to treat analysis means that all research subjects who have been randomized are included in the analysis according to their initial allocation regardless of whether or not the subject is taking the drug/therapy being tested or a placebo, or whether these subjects died before taking the drug being tested. Subjects who did not

failure.

take medication, lost to follow-up, and who moved to another group, are considered failures of their original group.

Whereas per protocol analysis only includes subjects who complete the research to the end.

- 4. Analysis of the difference in time to achieve a decrease in seizure frequency with the chisquare test or if it does not meet the requirements, an alternative test is performed, namely the Mann-Whitney test
- 5. Analysis of clinical characteristics, side effects of OAE, and laboratory findings of complete blood count (hemoglobin, hematocrit, leukocytes, platelets, and type count), liver function (SGOT and SGPT), kidney function (urea and creatinine), and blood electrolytes (sodium, potassium, calcium, chloride) in pediatric epilepsy patients who are resistant to combination second OAE who re-use first line OAE as substitution therapy and who use standard therapy (secondary outcome). All existing data is processed and presented in a table consisting of mean and standard deviation or median and inter-quartile range, as well as frequency distribution.
- 6. Analyzing factors that affect the decrease in the frequency of late seizures (age, seizure onset, seizure type, family history of seizures, developmental delays, history of OAE, initial seizure frequency, initial EEG, brain structural abnormalities) in pediatric patients with resistant epilepsy combination of second line OAE who re-use first line OAE as substitution therapy (secondary outcome).

Data is categorical. Data is analyzed using Chi-square statistical test, if results do not meet the requirements then an alternative test will be performed, known as Fisher's multivariate test and further analyzed with multivariate test and logistic regression analysis. The significance level (α) is 5% and the research confidence level is 80%. Results will show statistically related if value of $p \le \alpha$ is obtained.

Ethics and dissemination

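### Safety is in the title, aim and design statement, but the plan prespecifies no between-arm estimate of side effects and names no safety analysis set

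*Combined protocol and SAP*

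**What the plan says.** The title names efficacy and safety, and so does the Study Design section. The Introduction closes with the aim: "The study aims to analyzed the efficacy and safety of first-line AEDs as substitution therapy in drug-resistant epilepsy children".

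The Secondary Objectives split the work. Differences between the groups are to be analysed for quality of life, EEG and time to seizure reduction. For safety, "the research will describe the clinical characteristics, adverse effects of the drugs and laboratory features related to the adverse effects".

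Outcome evaluation, item d, follows that wording: "Description of drug side effects in the form of frequency distribution and percentage of side effects in each group". Statistical Analysis, item 5, covers clinical characteristics, side effects and laboratory findings as a secondary outcome, "presented in a table consisting of mean and standard deviation or median and inter-quartile range, as well as frequency distribution". It names no difference, ratio, interval or test, and no population.

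The one risk difference in the plan is item 3, introduced with "To assess drug effectiveness, the analysis used was the difference in actual failure". The event it counts is an increase in seizure frequency.

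**The concern.** A reader of the title and aim expects the randomised comparison to say something about relative safety. The plan as written gives two columns of percentages, to be compared by eye. With about 50 children per arm, that can make a chance difference look like an excess of reactions. It can also make similar percentages look like evidence of equal safety when the data are compatible with a sizeable difference either way.

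The missing analysis set adds to this. If the table is built from children who finish, those who left early drop out of the safety summary, and some may have left because of reactions. In an open-label trial, leaving the contrast and the population open also allows both to be chosen after the results are seen.

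**Working it through.** **1. Which outcomes have a between-arm method (Statistical Analysis section)**

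- Item 1, responders and EEG: chi-square or a Fisher test.
- Item 2, quality of life: unpaired t test or Mann-Whitney.
- Item 3, failure: absolute risk reduction on increased seizure frequency.
- Item 4, time to seizure reduction: chi-square or Mann-Whitney.
- Item 5, side effects and laboratory findings: a summary table only.

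Item 3 does not fill the gap, because its event is a seizure outcome and it is labelled effectiveness.

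**2. Which children are counted**

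The intention-to-treat and per-protocol definitions follow item 3 and refer to that test. Item 5 has no equivalent. Under Study procedure, children whose intervention is ended are classed as non-responders and dropped out. Under Discontinuation of study participation, the investigator may withdraw a child who did not get as far as tapering-off. Item 5 does not say whether either group stays in the safety table.

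**3. The plan's own figure**

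There is none for safety. The only sizing is for responders. The printed formula with its printed inputs (1.96, 0.84, P = 0.825, Q = 0.175, P1 = 0.95, Q1 = 0.5, P2 = 0.7, Q2 = 0.3, difference 0.25) gives 48.9 against the printed 49.56, taken as 50 per group. That depends on the printed Q1 of 0.5, although 1 − 0.95 = 0.05; this is a separate matter and does not affect the present point. I take n = 50 per arm as planned.

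**4. Precision of a between-arm estimate**

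The documents give no reaction rates, so I assume a range. With the same true rate p in both arms, the 95% half-width is 1.96 × √(2p(1 − p)/n):

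- p = 5%: 1.96 × √(2 × 0.05 × 0.95/50) = 8.5 points
- p = 10%: 11.8 points
- p = 20%: 1.96 × √(2 × 0.2 × 0.8/50) = 1.96 × 0.08 = 15.7 points
- p = 30%: 18.0 points
- p = 40%: 1.96 × √(2 × 0.4 × 0.6/50) = 19.2 points

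At 55 per arm (the 110 in the Sample size section), the half-width at 20% is 15.0 points.

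**5. What the interval adds to raw percentages (illustrative counts)**

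The Newcombe limits are d − √((p1 − l1)² + (u2 − p2)²) and d + √((u1 − p1)² + (p2 − l2)²), where l and u are the Wilson limits of each arm. These are 0.276 to 0.538 for 20/50 and 0.112 to 0.330 for 10/50.

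- 20/50 v 10/50: d = 0.20. Lower: 0.20 − √(0.124² + 0.130²) = 0.020. Upper: 0.20 + √(0.138² + 0.088²) = 0.364. The difference is 20 points, interval 2.0 to 36.4.
- 15/50 v 10/50: 10 points, interval −7.0 to 26.3. A table showing 30% and 20% could be read as an excess.
- 10/50 v 10/50: 0 points, interval −15.7 to 15.7. A table showing 20% and 20% could be read as equal safety.

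**6. Why no significance claim**

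Power of a two-sided 5% test at 50 per arm is Φ((Δ − 1.96 × √(2p̄(1 − p̄)/n))/√((p1(1 − p1) + p2(1 − p2))/n)), with p̄ the mean of the two rates. From an assumed 20%:

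- A rise of 10 points: (0.10 − 1.96 × 0.0866)/0.0860 = −0.81, power 21%.
- A rise of 20 points: (0.20 − 1.96 × 0.0917)/0.0894 = 0.23, power 59%.

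**The case against.** The strongest reply is that the plan is consistent with itself. The secondary objective says describe, outcome d describes, and item 5 tabulates. That stands: item 5 is not an error against its own objective. The mismatch is with the title, the aim and the design statement, which promise more than a description.

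A second reply is that a reader could subtract the percentages and compute an interval. That also stands if the table counts children. So it would go too far to infer that the trial cannot conclude anything on relative safety. What is missing is a prespecified estimate, its uncertainty and its population.

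Two stronger readings are tempting and not supported:

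- A reader might infer that the background predicts a tolerability difference between these arms, since it says "newer AEDs were not different in controlling seizures but have better tolerability, particularly fewer neurotoxic adverse effect". That sentence concerns newer drugs as a class. The Introduction lists topiramate, levetiracetam and oxcarbazepine as newer agents. The control arm takes oxcarbazepine for focal epilepsy but lamotrigine or clobazam for generalised epilepsy, and neither of those two is listed. Levetiracetam or topiramate is the drug being replaced. The only numerical difference the plan assumes is in efficacy, 0.95 v 0.70.
- A reader might take the percentage in outcome d to have events, not children, as its denominator. Outcomes a and c use percentages of subjects, and outcome d repeats the same phrase for laboratory results, where it cannot be literal. Loose wording is the likelier explanation.

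A third reply is that the trial is not sized for safety. That is true, and it is a reason to show the interval. It also limits what the interval can deliver.

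**Conclusion.** The point holds as a cheap improvement. Safety is in the title, aim and design statement, while the plan prespecifies no between-arm estimate of side effects, no measure of its uncertainty and no safety analysis set. The primary efficacy analysis is unaffected.

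The size of the gap can only be illustrated. At 50 per arm, the 95% half-width runs from about 9 points at an assumed 5% reaction rate to about 16 at 20% and 19 at 40%. Imprecision is therefore not confined to rare reactions. These figures assume 50 children per arm in the safety set, equal true rates and one count per child. Children who stop early are also observed for less time, which a simple risk difference does not adjust for.

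**What to change.** In Statistical Analysis item 5 and Outcome evaluation item d:

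- Define the safety set as all randomised children who took at least one dose of the substitution drug, including those later dropped out.
- Count each child once. Report by arm the number and percentage with at least one adverse reaction and with each commonly seen reaction type.
- For each, give the first-line minus second-line risk difference with a 95% confidence interval (Newcombe, for example), as an estimate without a significance claim.
- State that the arms will not be described as similarly safe on the strength of raw percentages alone.

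The cost is a few sentences and one extra column in a table already planned. Daily diary cards and the two-weekly visits already collect adverse reactions, so no new data, visits or patients are needed. The downside is that the intervals will be wide even for common reactions, and the report should say so plainly. Laboratory findings can stay tabulated as planned.

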This protocol is intended for a multicenter open label experimental, randomized controlled trial on the efficacy and safety of using first line AEDs as substitution therapy in childhood drug-resistant epilepsy. It will prospectively follow 100 children up during 14 weeks that consist of baseline, intervention, and post-intervention phases. While the intervention consists of 6 steps, as described at the Figure 1 below.

[figure not shown]

Figure 1. Timeline of the intervention phases

The study will be conducted at pediatric outpatient clinic of 3 referral hospitals in Jakarta, Cipto Mangunkusumo Hospital, Harapan Kita Hospital and Fatmawati Hospital. Children who are diagnosed with drug-resistant epilepsy receiving levetiracetam or topiramate will be enrolled in the study. Enrollment begins as soon as the research ethics committee approval is obtained from The Ethics Committee of The Faculty of Medicine, University of Indonesia-Cipto Mangunkusumo Hospital. The study will be closed after the last recruited patient has been followed up for the required 14 weeks.

All recruited children will be examined for monitoring at the hospital where the intervention is initiated. To avoid selection bias, all patients who met the inclusion criteria are divided into two groups, the intervention and control groups. Prospective participants and their parents will be provided with information related to the study. Patients will then fill out an information sheet containing demographic data, comorbidities, developmental history, school history, history of drug consumption, as well as history of seizures and patient complaints. All the data will be extracted and recorded on the case report form. Patients and their parents should be informed that participation is voluntary and they are free to withdraw from the study at any time. They should also be informed that refusal to participate or withdraw from the study will not affect the quality of treatment received. In the event of their withdrawal, it will be explained that the data collected so far is irrevocable, and we will seek consent to use such data in the final analysis if necessary.

Study procedure

Study procedures are depicted in Figure 2. The patients who are eligible for the study and have given their consents, will be enrolled, divided into 2 groups, the intervention and control, then start the 3-day baseline phase. In this phase, data such as demographic, clinical characteristic

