including seizure frequency, seizure type, seizure onset, medication history, family history of seizure, and also developmental stages, will be recorded from electronic medical record. Besides, the CT-scan or MRI are also collected from the same source. After that, their quality of life will be assessed by QOLCE-55 validated questionnaire through self-guided report. Furthermore, the laboratory investigation and EEG will be performed.

The next phase is intervention phase, started from initial step and ended by the maintenance of new combination therapy, which takes with overall 12 weeks. Initially, the substitution drugs with each initial dose are consumed. The drugs consist of valproic acid for the generalized and carbamazepine for focal epilepsies. On the other hand, the control group will take lamotrigine or clobazam for generalized and oxcarbazepine for focal ones. The phase continuous to titration dose, in which, the dose is raised gradually until it causes 50% of seizure reduction, and the next step is maintained the dose for about 2 weeks.

The following is tapering-off and after that stopping the substituted drug, levetiracetam or topiramate, which is determined by considering individual condition. Yet, if the seizures increase more than one and a half time of the previous frequency during the phases, the intervention will be ended immediately. On the contrary, if the condition is better, then the children go to the maintenance of new combination, that is the substitution drug and the old drugs in which the seizures do not go up or even better keep going down. The children who complete all of the phases are categorized as responder. In case if the intervention is ended, the subjects will be given the former combination therapy with adjusted doses in order to decrease the seizures until reaching the pre-intervention condition. The subjects are categorized as non-responder, and will be dropped-out. The other criteria of drop-out are resignation, non-compliance of study procedure, and death in term of other causal not related to the study. While in term of lost to follow-up, is intended for those who do not attend the study without any possible reasons.

[figure not shown]

Figure 2. flow-chart of the study

Maintenance the dose of the new combination therapy that consist of the new drug and

Maintenance

old drug after stopping the substituted drug

Inclusion criteria

- 1. Children age at 1 18 years old

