The test is performed in hospitals' laboratory where the study take place and is done twice, at the baseline and post intervention phase. The order of the blood test consists of complete blood test, liver function test including alanine and aspartate transaminase, kidney function test including urea and creatinine, and also blood electrolyte that consist of natrium, kalium and calcium. The laboratory professional takes the blood from vein of the arm. The subjects are seated or lying down, accompanied by the parents, while for the younger children, they seat on his/her parents' lap or position that make them feel comfortable. Older children may be asked to make a fist and then will be tied by a rubber band around his/her arms. After that, the needle is inserted the needle until the blood is drawn. The laboratory worker will take the needle since the amount of blood is enough and puts an adhesive bandage over the site. The next step is analyzes of the sample and the result will be issued for about 1-2 days both printed or provided on the electronic medical record.

Electroencephalography Examination

The EEG examination is operated two times, at the baseline and post intervention phase, with high density machine (Caldwell Easy III) is done twice, pre- and post-intervention. The machine will operate for about 45 minutes including 5 minutes each for eye-open and eye-close in every subjects. Beginning with acquisition, EEG recordings use standard parameter to analyze brain activity at various frequencies to gain good quality and artefact-free result. The printed results of the EEG is available for about 4-7 days after the examination.

Data collection

All relevant data will be recorded, by nominated member(s) of the research team, on a case report form (CRF). Each participant will have a CRF and be assigned a unique identification number.

Baseline data

At entry into the study, the following baseline information will be recorded in the CRF:

- unique patient identification number contact telephone number and/or email address
- date of entry into the study
- eligibility for study entry based on inclusion/exclusion criteria
- age at study entry, in years and months
- gender
- weight and height
- seizure type (eg, generalized tonic clonic, absence, myoclonic and partial)
- the age at diagnosis and duration of epilepsy
- seizure frequency or average number of seizures per month

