- current anticonvulsant(s) with doses and formulation and its side effect (if presents)
- other medications and its side effect (if presents)

- first recognized seizure date
- prior EEG and laboratory which has been performed at the baseline phase
- physical examination

Follow-up data

Follow-up data will be collected during regularly scheduled clinic visits (per 2 weeks). This information will be obtained from the participants' diary card. Important information to be collected at follow-up will include:

- physical examination
- adverse drug reaction of the substitution therapy that happen
- seizure's frequency
- type of seizure
- complaint

Outcome evaluation

- a. The difference in responders was the difference in the percentage of responders in the group that used first line OAE again as substitution therapy and those that used standard therapy. Responders are subjects who experience a decrease frequency of seizure more than or equal to 50% of the initial seizure. Frequency of seizure is the number of seizures that occur within 1 month. In previous studies, it was said that the frequency of seizures was said to have decreased significantly or was said to respond if the seizures were reduced by 50% or more from the initial seizure. ^{19, 29} Based on this, researchers will categorize the frequency of seizures into:
 - Responder: there is a decrease in the frequency of seizures by 50% or more than before
 - Non-responder: namely the frequency of seizures remains or decreases but not up to 50% of the initial seizure frequency or the frequency is more than before

Furthermore, the proportion in the form of the percentage of respondents in the two groups is calculated and differentiated, therefore it is classified into two groups:

- Different : when a significant difference is shown in difference of proportion test of the 2 unpaired groups.
- Not different: when there is no significant difference is shown in difference of proportion test of the 2 unpaired groups.

- b. Differences in quality of life: quality of life assessment using QOLCE-55 instrument. The average of each function (cognitive, emotional, social and physical functions) and the average of the total functions are assessed. This variable is categorized into:
 - Different, if there is a difference in the average quality of life
 - Not different, if there is no difference in the average quality of life
- c. Differences in electroencephalography appearance

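### Initial seizure frequency is tested as a factor for a 50% fall from that same initial frequency, so chance error in the baseline can produce a false association

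*Combined protocol and SAP*

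**What the plan says.** Outcome evaluation a defines the outcome against the baseline: "Responders are subjects who experience a decrease frequency of seizure more than or equal to 50% of the initial seizure". The unit follows: "Frequency of seizure is the number of seizures that occur within 1 month". Change in seizure frequency is then split into two categories, the upper one being "Responder: there is a decrease in the frequency of seizures by 50% or more than before".

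Outcome evaluation e names the factors to be related to the decrease, including "family history of seizures, developmental delay, history of OAE, initial seizure frequency, initial EEG, structural brain abnormalities". Statistical Analysis item 6 repeats the list ("history of OAE, initial seizure frequency, initial EEG, brain structural abnormalities") and restricts the analysis to children given first-line drugs as substitution. It treats the data as categorical, applies chi-square or Fisher and then logistic regression, and calls a factor related when p is at or below 5%.

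On the baseline itself, the case report form takes "seizure frequency or average number of seizures per month" (Baseline data) with no averaging window. Under Study procedure, seizure frequency is among the data that "will be recorded from electronic medical record", and children "then start the 3-day baseline phase" after allocation. No separate baseline period for the predictor, and no allowance for regression to the mean, is described.

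**The concern.** A child is a responder when the follow-up count is at most half the recorded initial count. If the recorded initial count is high by chance, the child moves up on the predictor, and the threshold for response also becomes easier to meet. If it is low by chance, the reverse happens. The association this creates runs in one direction: frequent seizures look more responsive. Logistic regression does not remove it, because the shared error stays on both sides of the model. None of the other eight factors has this link by construction. In the logistic model they are affected only so far as they correlate with initial frequency.

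At stake is a plausible but possibly false statement, from a named secondary analysis that the sponsor plans to publish, about which children do well on first-line substitution.

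**Working it through.** **1. The plan's own figure.** The documents compute nothing on this point. The only relevant figure is the arm size. The printed sample-size expression is ((1.96√(2×0.825×0.175) + 0.84√(0.95×0.5 + 0.7×0.3))/0.25)². It evaluates to ((1.053 + 0.695)/0.25)² = 48.9, against the stated 49.56, rounded to 50. (The printed Q1 of 0.5 should be 1 − 0.95 = 0.05; that is a separate matter.) Item 6 covers one arm, so about 50 children.

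**2. Why a link arises without any effect.** Let t be a child's true log rate, d the log change on treatment (independent of t), and e1 and e2 the chance errors at baseline and follow-up, each with variance v.
- log X = t + e1 and log Y = t + d + e2
- log fall: D = log X − log Y = e1 − e2 − d
- Cov(log X, D) = v, which exceeds 0 whenever the baseline has error
- With Var(log X) scaled to 1: correlation = v / √(2v + Var(d))

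If 80% of the baseline variance is real (v = 0.2) and Var(d) = 0.36, the correlation is 0.2/√0.76 = 0.23. If 95% is real (v = 0.05), it is 0.05/√0.46 = 0.07. The direction is fixed; the size depends on baseline error.

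**3. Size under item 6's test.** Simulation: 50 children, 6,000 trials per scenario, initial frequency split at the median, chi-square at 5%, responder if follow-up ≤ 0.5 × initial. All rates are assumptions, since the documents give none:
- median true rate 8, 20 or 60 a month
- between-child SD of log rate 0.5 or 1.0
- month-to-month overdispersion 0 (Poisson), 0.3 or 0.6
- median rate ratio on drug 0.4 (log SD 0.6), drawn independently of the true rate
- baseline window one month or a three-month average

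Percentage of trials with p ≤ 0.05 (range over the three median rates; nominal 5%):

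| Baseline window | Between-child log SD | Poisson | Overdispersion 0.3 | Overdispersion 0.6 |
|---|---|---|---|---|
| 1 month | 1.0 | 6.5-8.7 | 23.0-28.4 | 36.1-51.0 |
| 3-month average | 1.0 | 5.9-6.8 | 8.9-9.4 | 12.1-14.0 |
| 1 month | 0.5 | 6.1-17.5 | 53.5-55.0 | 67.1-77.4 |
| 3-month average | 0.5 | 5.9-8.0 | 16.2-17.9 | 25.8-27.1 |

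Central case (median 20, log SD 1.0, overdispersion 0.3, one month): 68.6% of the high-baseline half respond against 51.1% of the low half. The false odds ratio is (0.686/0.314)/(0.511/0.489) = 2.1, and 26.9% of trials reject.

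A further independent simulation, with overdispersion 0.3-0.5, gave about 24-40% for one month, 8-13% for a three-month average and 5-10% for Poisson variation only. These ranges fit the wider between-child spread in the table (log SD 1.0); a narrower spread gives higher rates.

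**4. Isolating the cause.** With the predictor taken from a separate period of the same length, and nothing else changed, rejection falls to 5.1-7.0% over all 36 scenarios. In the central case it is 5.8%, with 59% of the high half and 60% of the low half responding. The excess therefore comes from the shared baseline value.

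**The case against.** **The baseline may be a long average, in which case the effect is small.** The case report form allows a monthly average, the source is the chart, and entry requires at least three months of combination therapy. A multi-month average is a fair reading, and under it the excess is modest (8-13% in the headline range). With responder rates near the plan's assumed 95%, a three-month average and overdispersion 0.3-0.5, rejection was only 1-4%. This stands as a limit on size. But the window is not fixed, and the stated unit is one month.

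**Item 6 does not restate the 50% rule.** True. The link is inferred: item 6 analyses a decrease as categorical data, and Outcome evaluation a gives the only categories for change in frequency. Study procedure also labels children who complete all phases as responders. That rule too depends on reaching a 50% reduction during titration, so it does not clearly remove the link. The two definitions must be reconciled.

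**Stronger readings the documents do not support.**
- A reader might infer that initial frequency is tested against itself. It is not: the outcome also contains an independent follow-up count, and only the shared baseline error matters.
- A reader might infer that the trial will report a false predictor. Even at 40%, six trials in ten would not.
- A reader might apply error rates for 100 children. Item 6 is limited to the first-line arm.
- A reader might model no effect as the same 40% fall in every child. That null is not neutral: the chance of crossing 50% then depends on the true rate through counting noise. An independent month as predictor gave odds ratios of 0.7-0.9, and with Poisson noise at medians of 10-20 even the coupled odds ratio was 0.5-0.9, the reverse direction.

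**Conclusion.** The concern holds. As written, item 6 and outcome e can produce a false association between initial frequency and response, and nothing in the plan guards against it. With response independent of the true rate, the direction is that children with more seizures look more responsive.

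The size is not known. Roughly 24-40% false positives for one overdispersed month, 8-13% for a three-month average and 5-10% for Poisson variation rest on assumed seizure rates, within-child variation, between-child spread and a median split, none of which the documents give.

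The scope is one of nine factors in a secondary analysis. A reader might infer that the responder comparison between arms is also compromised. It is not: both randomised arms are measured against their baselines in the same way, so this mechanism does not bias the primary comparison.

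**What to change.** In Statistical Analysis item 6 and Outcome evaluation e, do not test initial seizure frequency against the responder outcome. Choose one of two replacements:

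1. Drop it from the tested factors and tabulate response by initial frequency descriptively, with a note that regression to the mean alone can produce a gradient.
2. Keep it, but take the predictor from an earlier chart period that is not used as the responder denominator. In the simulations this brought the error rate back to about 4-8%. The charts are already a data source and entry requires at least three months of combination therapy, so an earlier period should usually be available.

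In either case, state the window over which the denominator is counted.

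The change is wording only; treatment, visits and sample size stay as they are. The cost is that one listed factor is no longer formally tested (option 1), or that a second chart period must be extracted (option 2).
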